#### 1.4 Rationale for the Study and its Purpose

Recovery from acute illness invariably takes time and is associated with increased risk of new acute illness, physical dependency and mortality (figure 1). Delayed or incomplete recovery is common and increases with the age of the patient and the duration and seriousness of the acute disease. Recovery time can vary between a few days in otherwise healthy subjects with influenza to months, years or never in elderly patients after major illness. During a typical episode of acute serious illness with hospitalization the patient will be treated as an inpatient during the initial recovery phase which will be followed by a prolonged period in a long-term care facility, rehabilitation institution or at home with home nursing. Younger patients may recover at home without additional care, but will often be unable to work, adding to the costs for society.

The cause of the need for extended time to recover has not been explored extensively in the scientific literature and is by some viewed as "self-explanatory" while others call for more research. Prompt and adequate treatment of the acute illness, supportive treatment with fluids and nutrition and early mobilization are key focus areas in every hospital that are known to improve patient outcome and shorten recovery time. To our knowledge, no "recovery-improvement drug" exists. We aim to include patients in ICU who are in this late stabile phase and administer NR or placebo from that point and onwards for 90 days. This is a completely novel approach to the recovery phase where NR may be seen as a "recovery-improvement pill".

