#### 4.3 **Inclusion Criteria**

- 1. Adults > 18 years old, admitted to hospital with tissue damage, can be included when they are considered medically stable though still expected to remain hospitalized for at least 7 more days (from inclusion).
- 2. Preferably: Previously included in the Janus Cohort or any other cohort or study with stored biological samples.

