## **6 STUDY PROCEDURES**

## 6.1 Timing of investigations

Table 1: Timing of laboratory tests and biobanking

|                     |        | Inpatients |            |        |                  | Outpatients     |                    |
|---------------------|--------|------------|------------|--------|------------------|-----------------|--------------------|
|                     | Day 1* | Day 3 +/-1 | Day 7 +/-1 | Weekly | Day 90 +/-
10 | Withdrawl visit | Week 65
and 150 |
| Na                  | X      | X          | Χ          | Χ      | Χ                | Χ               | Χ                  |
| K                   | X      | Χ          | Χ          | Χ      | Χ                | X               | Χ                  |
| Calcium             | X      | Χ          | Χ          | Χ      | Χ                | X               | Χ                  |
| Mg                  | X      | Χ          | Χ          | Χ      | Χ                | Χ               | Χ                  |
| Phosphate           | X      | Χ          | X          | Χ      | Χ                | X               | Χ                  |
| Urea                | X      | Χ          | Χ          | Χ      | Χ                | Χ               | Χ                  |
| Creatinin           | X      | Χ          | Χ          | Χ      | Χ                | X               | Χ                  |
| GFR                 | X      | Χ          | Χ          | Χ      | Χ                | X               | Χ                  |
| Albumin             | X      | Χ          | X          | Χ      | Χ                | Χ               | Χ                  |
| Bilirubin           | X      | Χ          | Χ          | Χ      | Χ                | Χ               | X                  |
| CRP                 | X      | X          | Χ          | Χ      | X                | Χ               | Χ                  |
| ALP                 | X      | Χ          | Χ          | Χ      | Χ                | Χ               | Χ                  |
| ASAT                | Х      | X          | Χ          | Χ      | Χ                | X               | Χ                  |
| ALAT                | X      | X          | Χ          | Χ      | X                | X               | Χ                  |
| LT                  | X      | Χ          | X          | Χ      | Χ                | Χ               | Χ                  |

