|---------------------------------------|---|---|---|---|---|---|
| Total
Cholesterol                  | X | Х | Х | Х | Х | X |
| BIOBANKING:                           |   |   |   |   |   |   |
| 4x EDTA                               | X | Χ |   | Χ | Χ | Х |
| 1x Serum                              | X | Χ |   | Χ | Χ | Χ |
| 1x Plasma                             | X | X |   | Χ | Χ | X |
| 2x CPT                                | X | Χ |   | Χ | Χ | Χ |
| Urine, faeces, saliva,buccal swabs ** | x | x |   | x | x | х |

\* Prior to administration of intervention drug

Table 2: Timing of inclusion and procedures.

|                                      | Screening
period | Treatment Period At inclusion (1), day 3, 7 [i] And on discharge (DC) | Mid-
treatment
follow-up
phone call | Last week
of
treatment
visit at 90
days+/- 10 | End of
study
visit ca
65 wks. | Withdrawal
visit | Follow
up
period |
|--------------------------------------|---------------------|--|--|---|--|---------------------|------------------------|
| Screen patients [ii]                 | Х                   |  |  |   |  |                     |                        |
| Informed consent                     | Х                   |  |  |   |  |                     |                        |
| Inclusion + exclusion criteria       | Х                   |  |  |   |  |                     |                        |
| Medical history, prior treatment.    | Х                   |  | Х  |   |  |                     |                        |
| Treatment dispensed/returned         |                     | 1  |  | ×   |  | х                   |                        |
| Concomitant medication[iii]          | Х                   | 1-7, DC  | Х  | Х   | Х                                      | Х                   |                        |
| Physical examination [iv]            | Х                   | 1-7  |  | Х   | х                                      | Х                   |                        |
| Vital signs [v]                      | Х                   | 1-7  |  | Χ   | X                                      | Х                   |                        |
| Tests/questionnaires [vi] |                     | 1-7,   |  | Х   | Х                                      | Х                   |                        |

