#### 6.2 By Visit

Patients will be identified by the study staff screening patient records in collaborating wards. After conversation with the treating physician, a preliminary evaluation will be made regarding possible inclusion. After the patient has been thoroughly informed about the study and inclusion is deemed possible, all points mentioned in the above table will be carried out (flow chart 5.1). Informed consent must have been given voluntarily by each subject before any study specific procedures are initiated. Signed consent forms will be kept in a locked drawer inside the investigator's office.

Blood will be drawn early the following morning PRIOR to administration of NR/placebo. In addition to parameters mentioned in 5.1, NAD+ metabolites will also be measured. NR/placebo will be given shortly after this.

Staff at collaborating wards may contact the study staff out of hours.

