| Changes in hearing (clinical examination, portable audiometer, tympanometer and otoscopy | Changes in hearing thresholds from first week of inclusion compared to 90 days after inclusion.   |                                       |   |
| Antibiotic use   | Days on antibiotics after inclusion to end of trial   |                                       | Wilcoxon signed rank  |
| Antibiotic use 2   | Days from inclusion to first antibiotic free day  |                                       | Wilcoxon signed rank  |
| Highest CRP  | Highest CRP from inclusion to end of trial  |                                       | T test for average in intervention vs placebo group                 |
| Frailty  | 1) 4 meters walking test
and grip strength
measured at inclusion,
day 7, and at 90 days.
2) Clinical Frailty Score 2
weeks prior to admission
and at 90 days. |                                       | T test for average in intervention vs placebo group                 |
| Cognitive function   | Forward and backward recall, trail making test and MOCA at day 7* and 90 and week 65.   |                                       | T test for average in intervention vs placebo group                 |
| NAD+ metabolites   |   |                                       |   |
| Epigenetic age changes   | Horvath GrimAge,
Zhang, two of the most
relevant and newer
algorithms available at
the time of analysis   | end of treatment. Predictive power of | group and vs the
dedicated non-
hospitalized control
group |
| DNA methylation genome wide  Histone modifications                                       | Differentially methylated regions between baseline and end of study visit and between treatment groups See 9.5.4  |                                       | Genome wide significance.   |
| nistone modifications  | 366 3.3.4   |                                       |   |

\*Or on discharge if before day 7, or later if the patient cannot be tested on day 7.

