4.3 Baseline Patient Characteristics

 The patient demographics and baseline characteristics to be summarized include age in years, gender, ethnicity, body mass index, type of accommodation/level of care before admission, smoking status, level of frailty, Charlston score, in-hospital level of care, type of treatment during hospital stay (pressor, respiratory support, 02 supply), diagnosis, SAPSscore, degree of inflammation (highest CRP), mortality and morbidity (number of new organ failures).

Patient demographics and baseline characteristics will be summarized by randomised treatment arm and overall using descriptive statistics for continuous variables, and number and percentages of patients for categorical variables. There will be no statistical analysis of treatment difference. Any clinical important imbalance between the treatment groups will be noted.

5 Definitions of endpoints and Other Variables of Interest

Primary endpoint

Length of Hospital Stay

The length of hospital stay is defined as the number of days from commencing study treatment to medically fit for discharge from the hospital (to home, long term care facility or rehabilitation center or other facility with a lower care level). The term "Medically fit for discharge" is used instead of "discharge" to correct for extended stays due to logistical challenges (Example: medically fit for discharge, but no availability in long term facilities at that time). Only one patient was not discharged on the same day as she/he was medically fit for discharge). Admission to other hospitals after transfer from the first will be included in the total length of stay. The primary outcome will be the time from start of study treatment to discharge. Patients who die before discharge will be censored at the time of death.

Secondary endpoints (safety)

All-cause Mortality

All-cause mortality is a time to event outcome, with the date of randomization as the time when a patient becomes at risk. If a patient does not die during the study's follow-up, the observation is censored at the patient's last automated follow up.

New Infections

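### The highest-CRP endpoint counts the CRP drawn before the first capsule, which dilutes any NR effect on it

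*Protocol*

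**What the plan says.** In the table in Protocol 10.5.4 the variable is "Highest CRP from inclusion to end of trial" and the test is "T test for average in intervention vs placebo group". The row has no change score, no baseline covariate and no restriction to post-dose samples.

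Protocol 6.1 ("Table 1: Timing of laboratory tests and biobanking") schedules CRP on day 1, day 3, day 7, weekly in hospital, at day 90, at withdrawal and at weeks 65 and 150. The day-1 footnote reads "Prior to administration of intervention drug". Protocol 6.2 gives the same order after inclusion: "Blood will be drawn early the following morning PRIOR to administration of NR/placebo".

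On the state of patients at entry, Protocol 4.3 says they "can be included when they are considered medically stable though still expected to remain hospitalized for at least 7 more days", and Protocol 1.4 says "We aim to include patients in ICU who are in this late stabile phase". Protocol 4.4 excludes uncontrolled infection.

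The SAP defines no CRP outcome. Its outcome table (section 5) refers everything outside the main article back to the protocol, so the wording in 10.5.4 is the definition in force. SAP 4.3 lists "degree of inflammation (highest CRP), mortality and morbidity (number of new organ failures" among baseline characteristics and gives no time window.

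**The concern.** A maximum that includes an untreated value cannot fall below it. When a patient's CRP peaks on day 1, the endpoint is that value, whatever NR does afterwards. A real effect then appears only in patients whose post-dose CRP exceeds the day-1 value.

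Other rows of the same table avoid this. Respiratory support and ICU stay are counted from the first tablet or capsule, and NEWS is a change from a pre-tablet value.

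Inflammation is part of the proposed mechanism (Protocol 1.2 and 1.4.3). A null result on this endpoint could therefore be read as no anti-inflammatory effect when the endpoint had little chance of showing one.

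**Working it through.** **What the documents fix.** Inclusion comes first, then the day-1 blood sample, then the first capsule; the first scheduled post-dose CRP is day 3. That the window contains a pre-dose value needs no assumption.

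**What they do not give.** No CRP mean, SD, time course, effect or power is stated, so there is no figure of the plan's own to reproduce for this endpoint. The one design input used is the length-of-stay Weibull (scale 18, shape 2.2; Protocol 10.1). Its quartiles, 18 × (−ln(1−p))^(1/2.2), are 10.2, 15.2 and 20.9 days, which match the stated median of 15 and IQR of 10–21.

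**One patient (assumed values).** Day-1 CRP is 60 mg/L with a half-life of 5 days. Day 3 untreated is 60 × 0.5^(2/5) = 45.5; with a 30% NR reduction it is 31.8. The highest CRP is 60 in both cases, so the effect vanishes.

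**Simulation A.** Assumed: day-1 median 60 mg/L, log-SD 0.8, within-patient log-SD 0.3, a later flare in 10% or 30% of patients, stays from the planning Weibull, and a true post-dose factor of 0.70.

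| Half-life (days) | Flares | Day 1 is the maximum | Ratio of geometric mean maxima |
|---|---|---|---|
| 3 | 10% | 82% | 0.96 |
| 3 | 30% | 74% | 0.94 |
| 5 | 10% | 70% | 0.94 |
| 5 | 30% | 63% | 0.91 |
| 10 | 10% | 55% | 0.90 |
| 10 | 30% | 48% | 0.88 |

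The true ratio of 0.70 thus appears as 0.88 to 0.96, a reduction of 4% to 12%. Other assumed inputs widen this to about 2% to 12% while CRP is falling; with no decline the apparent reduction is about 20%.

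**Simulation B.** This uses a wider range of half-lives, residual log-SD 0.35, flares in 0% to 60% of patients, 40 NR v 18 placebo, and the unadjusted comparison of means. Retained share is the mean difference with the pre-dose sample divided by that without it; ranges run over the flare rates. The last two columns give the approximate chance of a significant result in NR's favour.

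| Half-life | Day 1 is the maximum (placebo) | Retained share | Pre-dose included | Post-dose only |
|---|---|---|---|---|
| 2 days | 68–87% | 9–48% | 3–6% | 21–24% |
| 4 days | 54–69% | 28–54% | 4–7% | 23–25% |
| 7 days | 44–56% | 39–59% | 5–9% | 24–26% |
| 14 days | 35–43% | 48–65% | 7–11% | 23–26% |
| No decline | 11–15% | 76–84% | 14–20% | 25–30% |

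Dilution occurs in every row. Its size depends on how fast CRP falls and how often it rises again.

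**Check on a tempting repair: day 7, or day 3 if discharged earlier.** Under the planning Weibull the share leaving before day 7 is 1 − exp(−(7/18)^2.2) = 12%. With a 33% shorter stay (scale 18 × 0.67 = 12.06) it is 1 − exp(−(7/12.06)^2.2) = 26%. About 14% more NR patients would then contribute a value from four days earlier. With no CRP effect, and stay independent of CRP, the NR geometric mean is inflated by exp(0.143 × 4 × ln 2 / half-life): about 14% at a half-life of 3 days and 4% at 10 days. The higher of day 3 and day 7 avoids most of this, because with falling CRP day 3 is usually the higher value whether or not day 7 was drawn. The distortion is about 0–3%.

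**The case against.** The strongest objection is that the size rests on invented CRP trajectories. That is correct. A reader might infer that day 1 is the peak for most patients. The documents do not support that as a fact: stable entry makes a falling CRP plausible, and in Simulation B the placebo share is below half at a 14-day half-life and with no decline. CRPs ordered in routine care may also count towards the maximum, and re-admissions and new infections are followed, so late peaks may be more frequent than assumed. What survives is that a pre-dose value is always included, and that dilution appeared in every scenario tried.

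Three further readings go too far.

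- **Baseline imbalance as bias.** Allocation is randomised, so chance imbalance in day-1 CRP is part of the t test's sampling error. It costs precision.
- **Longer stay, more samples, higher maximum.** Scheduled post-dose inpatient samples would average about 2.9 on placebo v 2.1 with a 33% shorter stay. But extra samples of a falling CRP rarely set a new maximum, and the shift in the endpoint is only about 0–3%.
- **The same quantity used as baseline and outcome.** Protocol 10.5.8 lists highest CRP descriptively beside severity items such as SAPS II at admittance, which suggests the index illness before inclusion. SAP 4.3 gives no window. The label is ambiguous; double use is not shown.

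It is also fair that little turns on this endpoint. SAP 2.4 confines hypothesis testing to the primary outcome, and SAP 1.2 keeps other protocol objectives out of the main publication.

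**Conclusion.** The point holds as a dilution problem. As written, the endpoint includes an untreated CRP for every patient and does not adjust for it. Under the assumed inputs, a true 30% post-dose reduction shows as roughly 2% to 12% if CRP is falling at entry and about 20% if it is not. These figures are illustrations, since no document gives CRP over time.

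A reader might infer that the comparison is biased, or that it is essentially one of baseline values. The documents support neither: randomisation rules out systematic bias from the pre-dose value, and how far that value dominates depends on an unknown trajectory.

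Severity is minor. This is one of many protocol secondary variables and lies outside the SAP's main-article outcomes.

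**What to change.** In Protocol 10.5.4, or in the analysis plan for the later articles, define the endpoint as the higher of the day-3 and day-7 CRP, both after the first capsule. Compare arms on the log scale with log day-1 CRP as covariate. Do not use day-7 CRP with day 3 substituted for patients discharged early, for the reason shown above. State which visit windows apply, because Protocol Table 1 and SAP 2.7 differ for days 3 and 7. In SAP 4.3, give the time window for highest CRP so that the descriptive variable cannot be confused with the outcome.

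The cost is wording only: the samples are already scheduled, and Protocol 10.4 allows changes to the plan until database lock. The loss is that CRP peaks after day 7 leave this endpoint; they remain visible through new infections and adverse events.

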### 10.5.5 Safety analyses

See SAP.

Tabular safety analyses will be performed for all collected variables.

#### 10.5.6 Exploratory analyses

#### Histone modifications and DNA methylation.

Our lab possess world leading ChIP-seq technology as evidenced by recent breakthroughs (Dahl, et al, Nature 2016) which we will use to connect the mechanism of action of NR to the clinical findings. The proposed mechanism of action of NR is restoration of intracellular NAD+ which is a rate limiting substrate for the epigenetic modifier SIRT1. SIRT1 is a lysine deacetylase which to large degree targets histones and thus acts as a genetic modifier directly affecting gene expression. We will do whole genome ChIP-seq analyses for the most important histone acetylations like H3K9ac and H4K16ac before and after treatment in all participants to identify which histones are differentially acetylated in the intervention group and to explore the genomic context of these histones.

#### 10.5.7 Other analyses (eg health economics, patient reported outcomes etc)

Economic costs per group will be calculated and compared.

#### 10.5.8 Descriptive statistics

The following variables will be analyzed descriptively:

Age

Gender

Ethnicity

**NEWS** score

Laboratory tests at inclusion

Vital measurements

Diabetes I

Diabetes II

Heart failure

Liver disease

COPD

Myocardial infarction

Peripheral vascular disease

Stroke/TIA

Dementia

Rheumatic disease/Connective tissue disease

AIDS

Type of housing before admittance

ECOG score before admission

All questionnaires used in baseline assessment.

Worst NEWS score

**Highest CRP** 

Respiratory support at during hospitalization before inclusion

Lowest GFR

Lowest blood Ph

Lowest MAP

Lowest Glasgow coma scale

SAPS II score at admittance

#### 11 STUDY MANAGEMENT

#### 11.1 Steering committee

A steering committee with representatives from participating departments will meet regularly during the study period to evaluate safety, administrative issues, progression, results and advice the PI on study related questions.

#### 11.2 Investigator Delegation Procedure

The principal investigator is responsible for making and updating a "delegation of tasks" listing all the involved co-workers and their role in the project. He will ensure that appropriate training relevant to the study is given to all of these staff, and that any new information of relevance to the performance of this study is forwarded to the staff involved.

#### 11.3 Protocol Adherence

Investigators ascertain they will apply due diligence to avoid protocol deviations. All significant protocol deviations will be recorded.

#### **11.4 Study Amendments**

If it is necessary for the study protocol to be amended, the amendment and/or a new version of the study protocol (Amended Protocol) must be notified to and approved by the the Ethics Committee.

### 12 Ethical requirements

The study will be conducted in accordance with ethical principles that have their origin in the Declaration of Helsinki and are consistent with ICH/Good Clinical Practice and applicable regulatory requirements. Registration of patient data will be carried out in accordance with national personal data laws.

#### 12.1 Ethics Committee Approval

The study protocol, including the patient information and informed consent form to be used, will be approved by the regional ethics committee before enrolment of any patients into the study.

The investigator is responsible for informing the ethics committee of any serious and unexpected adverse events and/or major amendments to the protocol as per national requirements.

The project has been approved by the Regional Ethics Committee with ID number: 2017/1334C.

#### 12.2 Trial registration and user Involvement

The trial was registered in www.clinicaltrials.gov during autumn 2018, and will be activated once inclusion of participants commences.

Users appointed by two patient's organizations have been involved in designing the study and will be involved in conducting the study.

